## SOCIAL PROTOCOL (HRP-580)

PROTOCOL TITLE: App-Assisted Day Reconstruction to Reduce Treatment Burden and Logistic Toxicity in Cancer Patients – Aim 1

VERSION DATE: 01/05/2023

and also happen to be from one of the groups checked above, they will be eligible to participate in the study.

## 11.0 Number of Participants

11.1 Number of Participants to be Consented: up to 30, 20 participants to complete interviews

## 12.0 Recruitment Methods

12.1 Recruitment Process:

CAB: CAB members will be recruited by study team members directly via phone calls and emails. This will not involve recruitment of MHealth Fairview patients.

Cancer Patients: [name] and study staff will identify potentially eligible participants in the clinic and/or through BPIC, who will review the electronic medical records of patients at MHealth Fairview using inclusion criteria. Patients who have opted out of research, including being approached for new studies, will not be contacted or approached. Potential participants will be approached in the clinic before or after a scheduled appointment and/or via MyChart using Fairview Research Services.

Research activities will not impact or interfere with patient's appointment times or clinical care. They will be given time to whether they would like to participate and provided information to contacting the study coordinator at a later time/date if they want to consider further.

12.2 Source of Participants: MHealth Fairview cancer clinics

12.3 Identification of Potential Participants: M Health Fairview medical records will be queried by BPIC to identify eligible individuals who have been diagnosed and treated for cancer within the past two years and who have not opted out of research.

12.4 Recruitment Materials: Mail recruitment documents for Aims 1 are provided.

12.5 Payment:

Each CAB member will be compensated \$500 for their 12-month project participation.

Interview participants will receive a \$50 gift card upon completion of the interview. Participants will receive an additional \$20 gift card for survey completion after evaluating the initial app design draft.

## 13.0 Withdrawal of Participants

13.1 Withdrawal Circumstances: No participant will be withdrawn from the study against their will. Participants will only be withdrawn from the study if they ask to withdraw or become too ill or die prior to completing the study. If participants become too ill,

## SOCIAL PROTOCOL (HRP-580)

PROTOCOL TITLE: App-Assisted Day Reconstruction to Reduce Treatment Burden and Logistic Toxicity in Cancer Patients – Aim 1

VERSION DATE: 01/05/2023

they will not be withdrawn from the study until they have given their voluntary consent for study withdrawal.

13.2 Withdrawal Procedures: If a participant chooses to withdraw at any point, their decisions will be respected without repercussions. Data collected until the point of withdrawal will be used unless the participant specifies otherwise.

13.3 Termination Procedures: Participants will not be terminated for any reason.

## 14.0 Risks to Participants

14.1 Foreseeable Risks: This study carries minimal risk and will comply with the University of Minnesota IRB reporting requirements. We identified the following 2 possible risks to subjects:

Risk to confidentiality: Inadvertent breaches of confidentiality by investigators or their staff are unlikely but may occur. Identifying information will be kept private and all identifiers will be removed prior to any data being given to researchers. The records will be identified only with a unique ID number on an encrypted database. Data transfer will only occur with de-identified data with encrypted transfer of all information containing protected health information between participants and study databases.

Discomfort while answering interview or survey questions: There is a possibility that some participants may feel uncomfortable answering interview or survey questions which may remind them of their cancer diagnosis. They will be reminded that they can skip any questions or discontinue at any time.

14.2 Reproduction Risks: N/A

14.3 Risks to Others: N/A

## 15.0 Incomplete Disclosure or Deception

15.1 Incomplete Disclosure or Deception: N/A

## 16.0 Potential Benefits to Participants

16.1 Potential Benefits: There are likely no direct benefits to individual participants.

## 17.0 Statistical Considerations

17.1 Data Analysis Plan:

Evaluating the interviews: Two coders will read the patient interview transcripts and identify themes grounded in the transcripts by using a computer-assisted qualitative data analysis system (NVivo) and applying the grounded theory approach and constant comparative method. Major categories in the classification system will be broad enough to remain relevant across contextual examples of logistic toxicity. Each major category will include subcategories to cluster specific activity examples.

## SOCIAL PROTOCOL (HRP-580)

PROTOCOL TITLE: App-Assisted Day Reconstruction to Reduce Treatment Burden and Logistic Toxicity in Cancer Patients – Aim 1

VERSION DATE: 01/05/2023

The patient interview data will also be used to develop user stories, an approach that is widely used in agile software development to identify key app requirements and provide good business cases for these requirements. Based on the interview findings, we will develop user interface sketches and app function narratives using established usability guidelines to illustrate functionality and appearance of the app.

Surveys will be scored using standard methods. Mean scores and score distributions will be evaluated.

### 17.2 Power Analysis:

A sample size of 20 participants will allow us to estimate the overall satisfaction rate with a margin of error of  $\pm 18\%$ .

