## 3.0 Study Endpoints/Events/Outcomes

3.1 Primary Endpoint/Event/Outcome:

Interviews: Identify themes to develop 1) a cancer-specific, multi-tiered activity/trip classification system to organize cancer treatment-related activities and trips in the app; and 2) user stories to describe what the users want to do with the proposed app.

Follow-up survey: Overall satisfaction with proposed system design will be measured using a 5-point Likert scale from not at all satisfied to very satisfied. The primary endpoint will be the proportion of participants who report an overall satisfaction score of 4.0 or above.

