## **SOCIAL PROTOCOL (HRP-580)**

**PROTOCOL TITLE:** App-Assisted Day Reconstruction to Reduce Treatment Burden and Logistic Toxicity in Cancer Patients – Aim 1

**VERSION DATE:** 01/05/2023

treatment for cancer. After recruitment and obtaining informed consent, an interviewer trained by Drs. [name] and [name] will use a semi-structured guide including open-ended questions. Following review by the research team and CAB, the interview guide will be assessed after the first five interviews for any necessary changes. If significant edits are made, those interviews will be treated as pilot data and left out of the analysis. Interviews will be digitally recorded and transcribed verbatim.

After the system design, the 20 interview participants will be sent a follow-up survey (approximately 15 minutes) online via REDCap or paper via mail to review the user interface sketches and app function narratives. Participants will be asked to provide open-ended feedback as well as their satisfaction ratings with each user interface sketch and app function narrative using a 5-point Likert scale from not at all satisfied to very satisfied. For each participant, the satisfaction ratings will be averaged to derive an overall satisfaction score.

- 5.3 Follow-Up: Survey data will be collected.
- 5.4 Individually Identifiable Health Information: We will obtain written HIPAA agreement from participants and authorization to communicate via email if that is the participant's preference.

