## **20.0 Provisions to Monitor the Data to Ensure the Safety of Participants**

20.1 Data Integrity Monitoring. The PI will review all signed consent forms for completeness at the time of participant entry into the study.

Data collection will occur primarily using REDCap, which will be set up to ensure data are clean and ready for analysis. Reports within REDCap will be used to identify missing data.

20.2 Data Safety Monitoring. This study carries minimal risk and therefore the PI will assume responsibility for monitoring and reporting safety concerns/events to the University of Minnesota IRB. Events requiring prompt reporting include any adverse event that requires a change to the protocol or consent form, any unauthorized disclosure of confidential information, any unresolved subject complaint or any protocol deviation that resulting in harm or the unanticipated death of an enrolled subject.

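### Does the ±18% margin fail because the plan never fixes how many participants enter the satisfaction rate?

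*Combined protocol and SAP*

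**What the plan says.** Section 3.1 defines the survey endpoint: "The primary endpoint will be the proportion of participants who report an overall satisfaction score of 4.0 or above". Under section 5.2 the score is the average of a participant's own ratings of the sketches and narratives.

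Section 17.2 gives the precision: "A sample size of 20 participants will allow us to estimate the overall satisfaction rate with a margin of error of" ±18%. It states no confidence level, assumed rate or allowance for loss.

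On numbers, section 11.1 reads "up to 30, 20 participants to complete interviews". Section 5.2 has the interview guide reviewed after five interviews and adds: "If significant edits are made, those interviews will be treated as pilot data and left out of the analysis". It then says: "After the system design, the 20 interview participants will be sent a follow-up survey".

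On incomplete data, section 14.1 says of participants: "They will be reminded that they can skip any questions or discontinue at any time". Section 13.2 says: "Data collected until the point of withdrawal will be used unless the participant specifies otherwise". Section 20.1 says: "Reports within REDCap will be used to identify missing data". Section 17.1 plans mean scores and score distributions for the surveys, and section 17.3 is marked N/A. No section says how a participant with an interview but no survey enters the proportion, or whether interviews set aside as pilot data are replaced.

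**The concern.** A precision statement holds only for the number actually analysed, and the plan appears to leave that number open in two ways.

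First, the pilot rule can take 5 of 20 interviews (25%) out of the analysis. If those five people also left the survey, 15 would remain behind a margin computed for 20.

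Second, the survey is sent only after the system has been designed, to people in active cancer treatment whose participation runs over about five months (section 8.1). Some non-return is foreseeable. The 30 consents protect the count of interviews, not of surveys. A non-returner could be kept in the denominator as not satisfied or dropped from it, and the two choices give different rates. If the choice were made after the data were seen, the more flattering figure could be reported for a primary endpoint.

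**Working it through.** **Inputs.** From the protocol: n = 20 and ±18% (17.2), a cut-off of 4.0 (3.1), five possible pilot interviews (5.2), and up to 30 consents (11.1). Assumed, because the documents give none: the confidence level, the expected satisfaction rate and the number of surveys returned.

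**1. Reproduce the stated margin.** Half-width = z × √(p(1 − p)/n), with n = 20.

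- 95%, p = 0.80: 1.96 × √(0.16/20) = 17.5 points.
- 90%, p = 0.50: 1.645 × √(0.25/20) = 18.4 points.
- 95%, p = 0.50: 1.96 × √(0.25/20) = 21.9 points, which does not match.

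Two ordinary sets of assumptions round to 18, so the figure is not shown to be wrong for 20 participants.

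**2. Does the pilot rule reduce that 20?** Set the two sentences of 5.2 side by side. The exclusion applies to interviews. The survey goes to the 20 interview participants, and nothing removes anyone's ratings. The satisfaction rate in 17.2 comes from the survey. On the text as written, setting aside five interviews leaves the survey at 20 and the interview analysis at 15. If the team chose to replace them, 20 + 5 = 25 completed interviews would still fit under 30 consents, provided that no more than 5 consented people fail to reach an interview.

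**3. Effect of fewer returned surveys on the margin.** Under the normal approximation the half-width scales with √(20/n), so it is 18 × √(20/n) whatever assumptions produced 18.

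| Returned (assumed) | Scaled from 18 | 95%, p = 0.80 | 90%, p = 0.50 |
|---|---|---|---|
| 20 | 18.0 | 17.5 | 18.4 |
| 16 | 20.1 | 19.6 | 20.6 |
| 15 | 20.8 | 20.2 | 21.2 |

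Losing a quarter of the surveys costs about 3 points of precision.

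**4. Effect of the denominator on the estimate.** With m of 20 surveys missing and x scores at or above the cut-off, the two rates are x/(20 − m) and x/20. Their gap is the rate among returns times m/20.

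| Returned (assumed) | Satisfied (assumed) | Among returns | Among all 20 | Gap (points) |
|---|---|---|---|---|
| 17 | 14 | 82.4% | 70% | 12.4 |
| 16 | 13 | 81.3% | 65% | 16.3 |
| 15 | 12 | 80% | 60% | 20.0 |

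Of these, only the last gap exceeds 18. A different quantity is the full best-to-worst range over all 20, which is m/20, or 5 points per missing survey. It passes 18 at m = 4 (20 points).

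**5. Can a reader undo the choice?** Yes. Both rates and both bounds follow from three counts: surveys sent, surveys returned, and scores at or above 4.0. For 13 satisfied among 16 returned of 20 sent, the rate is 81.3%, the lower bound 13/20 = 65% and the upper bound (13 + 4)/20 = 85%.

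**The case for a change.** The strongest case for a change is that this is a primary endpoint whose denominator is nowhere written down, that loss before the survey is predictable from the plan itself, and that a few sentences would settle the matter at no cost in data. A 20-point difference between two defensible readings is larger than the margin the plan quotes. The status of pilot interviewees also decides whether the interview analysis rests on 15 or 20 people.

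Much of this stands: the rule is absent, and writing it down would be good practice. It carries less weight than it seems for four reasons.

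- The score is an average of a person's own ratings, so someone who returned nothing has no score. Counting those who have one is the natural reading and fits the planned score distributions. Treating a non-returner as dissatisfied is possible but not what the text dictates.
- Large non-return is an assumption. The plan works against it with a paper option added in revision 4, a separate $20 card for the survey (12.5), and ongoing checks of completeness by the coordinator and statistician (17.4).
- Nothing in the protocol hangs on the rate: there is no hypothesis, success threshold or go/no-go rule. Picking the kinder denominator would change no stated decision and would show in the counts.
- Consents were raised from 20 to 30 in revision 3 with the interview goal kept at 20, so there is some room to replace pilot interviews if the team wishes.

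**Conclusion.** No change to the plan follows. The protocol leaves two details unwritten: how unreturned or part-completed surveys are counted, and whether pilot interviews are replaced. No rule that it does state gives a wrong result. The ±18% is reproducible at n = 20 under common assumptions, and the pilot rule as worded does not reduce the survey sample. With 15 surveys analysed the margin would be about 20 to 21 points. The denominator could move the rate by about 12 to 20 points for 17 down to 15 returns. These return counts, the assumed rates and the confidence levels are illustrations, since the documents supply none of them.

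In a small descriptive study meant to guide app design, analysts can be expected to fill the gap sensibly by reporting the rate among returned surveys alongside the numbers sent and returned. That report is enough for a reader to see the effect of any other choice.

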### 17.3 Statistical Analysis: N/A

### 17.4 Data Integrity: Data integrity and completeness will be monitored on an ongoing basis by the study coordinator and statistician, using both the reporting tools provided by REDCap and the study/data management dashboard provided by Dynamica.

## 18.0 Health Information and Privacy Compliance

### 18.1 Select which of the following is applicable to your research:

- My research does not require access to individual health information and therefore assert HIPAA does not apply.
- I am requesting that all research participants sign a HIPCO approved HIPAA Disclosure Authorization to participate in the research (either the standalone form or the combined consent and HIPAA Authorization).
- I am requesting the IRB to approve a Waiver or an alteration of research participant authorization to participate in the research.
- An external IRB (e.g. Advarra) is reviewing and we are requesting use of the authorization language embedded in the template consent form in lieu of the U of M stand-alone HIPAA Authorization. Note: External IRB must be serving as the privacy board for this option.

### 18.2 Identify the source of Private Health Information you will be using for your research (Check all that apply)

**SOCIAL PROTOCOL (HRP-580)**

**PROTOCOL TITLE: App-Assisted Day Reconstruction to Reduce Treatment Burden and Logistic Toxicity in Cancer Patients – Aim 1**

**VERSION DATE: 01/05/2023**

I will use the Informatics Consulting Services (ICS) available through CTSI (also referred to as the University's Information Exchange (IE) or data shelter) to pull records for me

I will collect information directly from research participants.

I will use University services to access and retrieve records from the Bone Marrow Transplant (BMPT) database, also known as the HSCT (Hematopoietic Stem Cell Transplant) database.

I will pull records directly from EPIC.

I will retrieve record directly from axiUm / MiPACS

I will receive data from the Center for Medicare/Medicaid Services

I will receive a limited data set from another institution

Other. Describe:

18.3 Explain how you will ensure that only records of patients who have agreed to have their information used for research will be reviewed.

We will obtain information about potentially eligible patients through BPIC which will filter out patients who do not agree to have their records used for research.

18.4 Approximate number of records required for review: 3000

18.5 Please describe how you will communicate with research participants during the course of this research. Check all applicable boxes

This research involves record review only. There will be no communication with research participants.

Communication with research participants will take place in the course of treatment, through MyChart, or other similar forms of communication used with patients receiving treatment.

Communication with research participants will take place outside of treatment settings. If this box is selected, please describe the type of communication and how it will be received by participants.

Communication with participants will occur through phone calls and email based on participant preference for scheduling appointments and by email through REDCap or mail for survey completion. We will ask participants to complete an authorization to receive unsecured emails from study staff if they prefer that mode of contact.

## SOCIAL PROTOCOL (HRP-580)

PROTOCOL TITLE: App-Assisted Day Reconstruction to Reduce Treatment Burden and Logistic Toxicity in Cancer Patients – Aim 1  
VERSION DATE: 01/05/2023

### 18.6 Access to participants

Participants will complete consent and HIPAA forms prior to any data collection.  
After they agree to participate, all data will be provided by the participants.

### 18.7 Location(s) of storage, sharing and analysis of research data, including any links to research data (check all that apply).

In the data shelter of the [Information Exchange \(IE\)](#)

Store       Analyze       Share

In the Bone Marrow Transplant (BMT) database, also known as the HSCT (Hematopoietic Stem Cell Transplant) Database

Store       Analyze       Share

In REDCap (recap.ahc.umn.edu)

Store       Analyze       Share

In Qualtrics (qualtrics.umn.edu)

Store       Analyze       Share

In OnCore (oncore.umn.edu)

Store       Analyze       Share

In the University's Box Secure Storage (box.umn.edu)

Store       Analyze       Share

In an AHC-IS supported server. Provide folder path, location of server and IT Support Contact:

\\cancer.ahc.umn.edu\cancer\CancerCenter\Biostat\CCSG\[name]\Daynamica\_STTR\data

Store       Analyze       Share

In an AHC-IS supported desktop or laptop.

Provide UMN device numbers of all devices:

Store       Analyze       Share

## SOCIAL PROTOCOL (HRP-580)

PROTOCOL TITLE: App-Assisted Day Reconstruction to Reduce Treatment Burden and Logistic Toxicity in Cancer Patients – Aim 1  
VERSION DATE: 01/05/2023

Other.

Indicate if data will be collected, downloaded, accessed, shared or stored using a server, desktop, laptop, external drive or mobile device (including a tablet computer such as an iPad or a smartphone (iPhone or Android devices) that you have not already identified in the preceding questions

- I will use a server not previously listed to collect/download research data:
- I will use a desktop or laptop not previously listed
- I will use an external hard drive or USB drive ("flash" or "thumb" drives) not previously listed
- I will use a mobile device such as a tablet or smartphone not previously listed

### 18.8 Consultants. Vendors. Third Parties. N/A

18.9 Links to identifiable data: When patients agreed to participate, they will be given a study ID which will be used for the remainder of the study. The identifying information will be stored in REDCap (survey data collection) with the study ID and all other data will be stored using this ID alone.

18.10 Sharing of Data with Research Team Members. Data will be shared using Box and REDCap.

18.11 Storage of Documents: Paper consent forms may be collected during in-person recruitment. Paper documents will be stored in a locked cabinet in the PI's locked office. They will be stored up to 10 years.

18.12 Disposal of Documents: Following publication and dissemination (up to 10 years post study initiation), all paper documents will be shredded and all identifying information in REDCap will be removed.

## 19.0 Confidentiality

19.1 Data Security: All study investigators and staff will be fully trained on data safety and participant confidentiality using appropriate CITI and University of Minnesota courses. An electronic copy of the signed consent form will be stored on an AHC-IS supported server. The consent form and other research information will NOT be placed in the participants' medical record.

Electronic data will be entered by the study coordinator and will be stored on the secure REDCap database. Study data will be de-identified before data analysis. Only the researchers directly involved with the study will have access to the data. Identifying data will be stored until completion of the study and manuscript submission.

## SOCIAL PROTOCOL (HRP-580)

PROTOCOL TITLE: App-Assisted Day Reconstruction to Reduce Treatment Burden and Logistic Toxicity in Cancer Patients – Aim 1

VERSION DATE: 01/05/2023

## **20.0 Provisions to Monitor the Data to Ensure the Safety of Participants**

20.1 Data Integrity Monitoring. The PI will review all signed consent forms for completeness at the time of participant entry into the study.

Data collection will occur primarily using REDCap, which will be set up to ensure data are clean and ready for analysis. Reports within REDCap will be used to identify missing data.

20.2 Data Safety Monitoring. This study carries minimal risk and therefore the PI will assume responsibility for monitoring and reporting safety concerns/events to the University of Minnesota IRB. Events requiring prompt reporting include any adverse event that requires a change to the protocol or consent form, any unauthorized disclosure of confidential information, any unresolved subject complaint or any protocol deviation that resulting in harm or the unanticipated death of an enrolled subject.

